The proposed observational study will evaluate the relationship between measures of psychopathology, disordered eating, and impulsivity, (each assessed preoperatively and in the early postoperative period) and changes in weight and psychosocial status in the first two years after bariatric surgery. Secondary outcomes of prevalence and control of T2D and hypertension, health services utilization, and adherence to antidiabetes and antihypertensive medication will also be assessed. All participants will complete assessments at baseline (before surgery) and at 6, 12, and 24 months follow-up. Secondary aims will examine psychopathology, disordered eating, impulsivity, as well as weight loss, in relation to changes in eating behavior, physical activity, psychosocial status, and substance use in the first two years after bariatric surgery. The study has one specific aim and two secondary aims. Specific Aim 1: To determine the relationship between psychopathology, disordered eating, and impulsivity assessed preoperatively and changes in body weight over the first two years following bariatric surgery. We will determine which individual measures falling under these constructs are important in predicting the relative success of bariatric surgery. We will also examine the relationship of changes in the individual measures (from baseline to 6-months after surgery) on subsequent weight loss. (The study is powered on this aim.) We predict that individual measures of psychopathology, disordered eating, and impulsivity will predict smaller weight losses two years postoperatively. We also predict that smaller changes in measures of impulsivity, psychopathology, and disordered eating within the first 6 postoperative months will be associated with smaller weight losses at postoperative month 24. Secondary Aim 1: To examine the correlation structure among our individual measures, and subsequently will generate and confirm composite measures for the three constructs. Composite measures of psychopathology, disordered eating, and impulsivity will predict smaller weight losses two years postoperatively. We also will estimate the proportion of variance in weight loss accounted for by each composite measure. We predict that confirmatory factor analysis will confirm that our individual measures represent three constructs of psychopathology, disordered eating, and impulsivity. Higher values of these composite measures will in turn predict smaller weight losses at postoperative month 24. Secondary Aim 2: To assess the relationship between baseline measures of interest and postoperative changes in caloric and macronutrient intake, eating behavior, physical activity, and psychosocial status. We predict that participants with greater psychopathology, disordered eating, and impulsivity will report greater caloric intake, less favorable changes in macronutrient intake and eating behavior, participate in less physical activity and report more symptoms of psychosocial distress.

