
greatest risk for new onset SUDs were more likely to report problems with high sugar/low fat food before surgery, further suggesting the role of impulsivity in eating behavior and substance use before and after surgery.110 This increase in substance abuse after surgery has been described as addiction transfer111 and characterized as a modern example of symptom substitution in which abuse of one substance (food) is replaced by another (alcohol or drugs) when patients are unable to consume large amounts of food after surgery.109 A potential contributor to addiction transfer may be emotional dysregulation. In general, symptoms of depression typically improve within the first six months of bariatric surgery as patients are in the period of most rapid weight loss.35 Within the first two postoperative years, the use of anti-depressant medications also decreases; however, a substantial minority of patients report using these medications two years after surgery. As most patients begin to regain weight postoperatively, they also experience an erosion of the improvements in depressive symptoms and quality of life.112 In addition, a higher-than-expected number of postoperative suicides have been documented.17,44 A secondary aim of the proposed study will investigate the relationship between changes in weight during the first two postoperative years and changes in psychosocial status. Summary The relationship between preoperative psychosocial status and postoperative outcomes is one of the holy grail issues in the area of bariatric surgery. Concern about preoperative psychosocial status is one reason that standard clinical practice in the United States requires that individuals who seek bariatric surgery undergo a preoperative psychosocial evaluation (typically a clinical interview that does not include a structured diagnostic assessment) prior to surgery. This evaluation is designed to identify potential psychiatric and behavioral contraindications to surgery (psychosis; severe, untreated depression; active substance abuse; or significant behavioral non-compliance) and also provide patients with psychoeducation on the dietary and behavioral challenges after surgery.113 Prior to surgery, patients also meet with registered dietitians who teach them the basic elements of the postoperative diet and behaviors required for optimal postoperative outcomes. These evaluations exclude relatively few patients for surgery.55,84,114-116 Patients with psychosocial and behavioral issues, such as mood disorders and disordered eating, often are recommended for surgery even in the presence of these concerns. There is some evidence to suggest that a substantial percentage of these individuals subsequently experience smaller than expected weight losses, weight regain, or psychosocial distress after surgery. Patients with a history of psychopathology, specifically those with mood disorders or disordered eating, are vulnerable to returning to maladaptive eating and activity behaviors which likely promoted the development of extreme obesity and may compromise long-term weight control. While investigations of the relationship between specific diagnoses and postoperative outcomes have shed some light on these relationships, we believe that a common psychological construct, impulsivity--an important element of overeating, substance use, and mood disorders--may be a robust predictor of postoperative outcomes along with psychopathology or disordered eating. Few studies have used objective tests of impulse control in individuals undergoing bariatric surgery. To fill this gap, the proposed observational study will evaluate the relationship between measures of psychopathology, disordered eating, and impulsivity, (each assessed preoperatively and in the early postoperative period) and changes in weight and psychosocial status in the first two years after bariatric surgery. Results of this study would provide important information on the role of psychopathology, disordered eating, and impulsivity on outcomes of bariatric surgery and underscore the need for more comprehensive assessment and management of these behaviors before and after surgery.

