
The following documents are currently attached to this item:

There are no documents attached for this item.

Deception

Does your project use deception? No

Analysis Plan

Analysis will be conducted using Stata 13.0 (Stata Corporation, College Station, TX). After the completion of quality assurance procedures, descriptive statistics will be summarized for all patients by predictor group (dichotomized). Data screening: Prior to performing analyses, standard data screening/ cleaning procedures will be applied. These procedures will: screen the data for data-entry errors; check for outliers; assess the extent and pattern of missing data; create all summary scores needed for analysis; and check that appropriate assumptions of normality are met. In all analyses, the assumptions underlying the application of all the statistical methods that are used will be examined, principally through the use of standardized residuals, influence diagnostics, and graphical displays. Image processing will include image quality assessment procedures that examine global and region of interest (ROI) based raw and processed temporal signal-to-noise ratio, absolute and relative motion, and signal spike count. Potential outliers will be identified in the cumulative sample by examining quality assessment measures and flagging for further investigation subjects greater than two standard deviations from the mean on any one measure (i.e., behavioral performance, image distortion and artifact, general linear model fit). The purpose of this evaluation is to determine whether the time series is likely valid, and, if so, it will remain. Otherwise it will be corrected, if feasible, or removed from the analysis. The final sample will be examined in a similar fashion to determine whether any subjects warrant data cleaning or require exclusion from the final statistical analysis. Analysis of repeated measures: Our four-session within-subject design will generate multiple outcome measures that belong to the Gaussian family, and we will therefore use standard repeated-measures analysis of variance (ANOVA). Imaging outcomes (perfusion and BOLD) will be modeled using standard voxel-based image analysis techniques (described below) that incorporate random effects. Other outcomes (weight loss, ratings) will be modeled using a linear mixed-effects models framework, using using Stata 13.0 (Stata Corporation, College Station, TX). We could use a population averaged approach such as generalized estimating equations. However, the mixed model approach will provide the flexibility to allow for different error variances for different sessions if necessary. Voxel-based image analysis has limited flexibility, particularly when adding multiple covariates and interaction. When needed, summary values (e.g., mean rCBF, mean BOLD% signal change) extracted from ROIs will be modeled in STATAs mixed-models framework. These models can be extended to include additional explanatory variables (e.g., weight change, heart rate, respirations, age). Primary Aim 1 We will take a mixed models approach. The main interest in this study is the Group x Time interaction, where Group will be a between-subjects factor and Time will be a categorical within-subjects factor. This can be interpreted as population averages (GEE fitting method). Hypothesis 1: We will fit a 2 (Group: Dichotomized Baseline Measures, Low, High) x 3 (Time: change from baseline to month 6, 12 and 24) mixed-effects model for change in weight. Hypothesis 2: We will fit a 2 (Group: Dichotomized difference scores, 6 Month minus Baseline, Low, High) x 2 (Time: change from baseline to months 12 and 24) mixedeffects model for change in weight. In addition, the mixed effects models will include adjustments for surgical procedure, gender, and time since surgery. We recognize that the change in weight could also be associated with effects of several pertinent patient characteristics. To this end, we will consider additional covariates (e.g. sociodemographic variables, comorbidities, medication use, tobacco use, and initial weight). For both hypotheses, we will explore the continuous version of our predictor variables, where in place of Group, we use the real values of the predictor. This yields a difference of slopes with respect to predictor value across time points. Secondary Aim 1 We will use confirmatory factor analysis to verify our expected natural groupings of individual measures into composite measures. We will specify 3 factors and use Varimax rotation. We will assemble composite scores for each of our constructs by summing the standardized score values. We will then standardize the composite score and outcome (change in weight at 24 months). We will estimate the partial correlations (direct and indirect) among individual measures, composites, and outcome in a path analysis as suggested by Figure 1 to estimate the fraction of variance in outcome accounted for by each of the constructs. Secondary Aim 2 The outcomes will consist of (continuous) changes in behavior from baseline. We will use correlation to examine the relationship of baseline impulsivity measures to changes at 6, 12 and 24 months. The exception is changes in diet composition. In this analysis, we will use multivariate regression methods,

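### Hypothesis 2 models weight change from baseline and leaves out month-6 weight, so its group differences at months 12 and 24 cannot separate later weight loss from loss in the same six months as the predictor.

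*Combined protocol and SAP*

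**What the plan says.** The aim is in Objectives, Overall objectives, Specific Aim 1: "We will also examine the relationship of changes in the individual measures (from baseline to 6-months after surgery) on subsequent weight loss". The prediction attached to it, stated for month 24, reads: "smaller changes in measures of impulsivity, psychopathology, and disordered eating within the first 6 postoperative months will be associated with smaller weight losses". The same section says the study is powered on this aim.

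The model is in Analysis Plan, Primary Aim 1, Hypothesis 2: "2 (Group: Dichotomized difference scores, 6 Month minus Baseline, Low, High) x 2 (Time: change from baseline to months 12 and 24". The plan names the group-by-time interaction as its main interest. Under Procedures (Weight), percent weight loss at every visit is calculated against baseline weight.

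On covariates, "the mixed effects models will include adjustments for surgical procedure, gender, and time since surgery". Beyond these, "we will consider additional covariates (e.g. sociodemographic variables, comorbidities, medication use, tobacco use, and initial weight". The only weight term named is initial weight. Under Primary outcome variable(s), weight change is measured at 0, 6, 12 and 24 months, so month-6 weight is available, and Hypothesis 1 uses it as an outcome. An earlier sentence in the Analysis Plan does allow weight change as an added explanatory variable. It follows the text on imaging summary values and does not specify the Hypothesis 2 model. The sensitivity analyses listed under Missing data offer no analysis that starts from month 6.

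**The concern.** The Hypothesis 2 predictor is not known until month 6, so loss that is subsequent to it starts there. The outcome starts at baseline, and its first six months coincide with the period over which the predictor is formed. If patients who lose more weight early also improve more on a measure, improvers will show greater loss from baseline at months 12 and 24, even if nothing differs between the groups after month 6.

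The Background gives some reason to expect such a link for at least one measure: "symptoms of depression typically improve within the first six months of bariatric surgery as patients are in the period of most rapid weight loss".

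At stake is the interpretation of a result from the aim on which the study is powered. A finding that early psychological change predicts later weight loss could be no more than two early changes happening together.

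**Working it through.** There is no planned figure to reproduce. The documents give 300 participants with a completed baseline visit but no alpha, power, effect size, standard deviation or dropout rate for this aim.

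**Step 1: compare the windows.**
- Predictor: months 0 to 6.
- Outcomes: months 0 to 12 and 0 to 24. Both contain months 0 to 6.
- Aim: loss after the predictor, that is, from month 6 on.
- Month-6 weight in the model: none named.

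**Step 2: inputs for the size.** From the documents: 300 participants. Assumed: a median split (150 per group), normal data, a two-sided 5% test, no dropout, and no relation between early change and weight after month 6. Let r be the correlation of 0-6 month improvement with 0-6 month weight loss, and rho the correlation of month-6 with month-24 weight loss. Both are best read as what remains after adjusting for procedure and gender.

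**Step 3: formula.** A median split of a normal predictor puts the two group means 2 x sqrt(2/pi) = 1.596 standard deviations apart. The standardised month-24 gap arising only through early weight loss is

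d = 1.596 x r x rho.

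Its standard error is sqrt(2/150) = 0.1155. The chance of a significant result is Phi(d/0.1155 - 1.96) + Phi(-d/0.1155 - 1.96).

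Worked case, r = 0.2 and rho = 0.65: d = 1.596 x 0.13 = 0.207; d/0.1155 = 1.80; Phi(-0.16) plus a negligible second term gives about 43.5%.

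**Step 4: month-24 gap, month-6 weight not in the model.**

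| r | rho = 0.5 | rho = 0.65 | rho = 0.8 |
|---|---|---|---|
| 0 | 5% | 5% | 5% |
| 0.1 | 11% | 15% | 20% |
| 0.2 | 28% | 44% | 60% |
| 0.3 | 55% | 77% | 91% |

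Simulation agrees within sampling error. Allowing for that error gives rounded ranges of 9-20%, 28-60% and 53-93%. With 120 per group (240 patients) the formula gives 10-17%, 24-51% and 46-84%.

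**Step 5: with month-6 weight loss as a covariate.** In the same simulated data the month-24 test rejects in 4.2-6.0% of studies. This result belongs to that data model; the objection below shows where it fails.

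**Step 6: the group-by-time interaction.** In Hypothesis 2 this is the group difference in change between months 12 and 24. If month-6 loss carries over equally to both visits, it cancels, and simulated rejection is 4.1-6.8%. If carry-over fades from 0.8 at month 12 to 0.5 at month 24, rejection is about 8-43% for r = 0.1-0.3. The sign is then reversed: improvers appear to regain weight. The fading figures also depend on an assumed residual correlation between the two visits.

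**The case against.** **The declared main contrast is the interaction.** This stands as a limit. A reader might infer that the distortion in Step 4 affects every Hypothesis 2 test. It does not: the percentages are for the month-24 gap only, and the interaction is either unaffected or pushed the other way. But the interaction does not test the stated prediction, which is about weight loss at month 24.

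**The association at month 24 is real.** In the simulated data improvers have lost more weight from baseline, so a significant result is correct for the prediction taken literally. It is a false positive only for loss after month 6. That is fair, and it is why the two questions need separate labels. The aim does use the word subsequent.

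**Month-6 weight may be a mediator.** If early improvement drives early weight loss, adjusting removes a genuine effect. Reversing that arrow gives much the same unadjusted rates (28-91% at r = 0.2-0.3) and about 5% after adjustment, so the calculation cannot distinguish bias from mediation. This stands.

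**Adjustment is not always safe.** Suppose early change affects month-6 weight, and an unmeasured factor affects weight at both month 6 and month 24 (assumed coefficients 0.6). The adjusted test then rejects in roughly 25-55% of studies at r = 0.2-0.3, with the wrong sign, although early change has no later effect except through month-6 weight. This stands, and it rules out treating the adjusted estimate as simply the right answer.

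**The evidence for r is thin.** The Background sentence describes an average time course for depression. It gives no between-patient correlation, and none for the impulsivity, alcohol or eating measures.

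**The covariate list is open.** Month-6 weight is unspecified rather than excluded. A covariate that changes the question should still be fixed in advance, not left for consideration.

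**Conclusion.** The point holds as a mismatch between aim and outcome. The aim concerns weight loss after the early change in the measures; the model analyses loss from baseline and names no month-6 weight term. The group differences at months 12 and 24 cannot tell the two apart. That conclusion follows from the text alone.

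The size is conditional. It ranges from no inflation at r = 0 to about nine studies in ten at r = 0.3 and rho = 0.8, and neither correlation is in the documents.

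Two stronger readings are not supported. One is that the plan would present early improvement as a cause of later weight loss: the study is described as observational, and its predictions are worded as association and prediction. The other is that month-6 weight is a proven confounder that must be removed: the documents do not settle whether it is a confounder, a mediator or both. The plan should be changed because it does not say which quantity Hypothesis 2 estimates.

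**What to change.** For the question about subsequent weight loss, prespecify a month-6 landmark version of Hypothesis 2. The outcome can be weight change from month 6 to months 12 and 24, or the present change from baseline. In either case include each participant's baseline-to-month-6 weight change and its interaction with Time as covariates, and state which group differences answer the month-24 prediction.

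Keep the present model, labelled as the total association with weight loss from baseline, and say that it does not separate early from later loss. Report both, and make no causal claim from either.

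The cost is analysis-plan wording; month-6 weight is already collected. The downside is that the landmark estimate leaves out any benefit acting through early weight loss and can be biased by unmeasured factors that affect weight at month 6 and later. That is the reason to show the two estimates side by side.
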